5.2.3. Key Secondary Estimand

The key secondary estimand is defined by the following components:

Population: patients with a pre-defined minimum threshold and fluctuation of depressive symptoms as captured by IDS-SR₃₀ score before randomization.

Endpoint: change in HAM-A total score from Baseline to the end of Week 6.

Measure of Intervention: the effect of the initially randomized treatment that would have been observed had all patients remained on their treatment throughout the double-blind phase.

Intercurrent events: early study discontinuation for any reason.

Summary measure: difference in treatment means.

5.2.4. Key Secondary Efficacy Analysis

HAM-A total score and change from Baseline will be summarized by treatment group and study visit. Change from Baseline in HAM-A total score will be analyzed using an MMRM model with fixed effects for treatment group, region, visit, and treatment group-by-visit interaction, a random effect for patient within treatment group, and Baseline HAM-A total score as a covariate. Comparisons against placebo will be performed using the appropriate contrasts from this model at Week 6.

As a sensitivity analysis of the primary endpoint, change from Baseline to Week 6 in HAM-A total score will additionally be analyzed using an ANCOVA model with factors for treatment and region and Baseline HAM-A score as a covariate. This analysis will be repeated for change from Baseline to Week 2 and 4 as well. For this analysis, patients missing HAM-A total score at any visit will have this value imputed using the LOCF method.

An additional sensitivity analysis of the primary endpoint will be performed to determine the impact of how data missing due to early discontinuation for any reason is handled. This analysis will use the same ANCOVA model described above. This analysis will be repeated for change from Baseline to Week 2 and 4 as well. For this analysis, any HAM-A total scores that are missing due to early discontinuation of a subject will be imputed using the value of the mean HAM-A total score in the placebo group at that timepoint. All missing HAM-A total scores that are not due to early discontinuation will be imputed using the LOCF method.

A final sensitivity analysis of the key secondary endpoint will be performed using the same ANCOVA model described above, wherein all missing HAM-A total scores will be imputed using multiple imputation. Missing values will be imputed using the following auxiliary information: treatment, Baseline HAM-A total score, region, sex, Baseline age, and visit. Treatment, Baseline HAM-A total score, region, sex, Baseline age, and visit are included as auxiliary information because it is believed that subjects with similar values for each of these parameters would respond similarly. A total of 10 imputations will be performed. The least square (LS) Mean, standard error (SE), LS Mean difference and p-value from the PROC MIANALYZE will be presented. Additionally, the range of p-values from all 10 imputations will be presented.

5.2.5. Additional Secondary and Exploratory Endpoints

Other secondary and exploratory endpoints include

- Change from Baseline in CGI-S score
- Observed CGI-I score
- Change from Baseline in IDS-SR₃₀
- Change from Baseline in SHAPS
- Change from Baseline in DSST
- Change from Baseline in PSS
- Change from Baseline in A-SEX
- Rate of MADRS responders
- Time to $\geq 50\%$ MADRS improvement
- Time to $\geq 30\%$ MADRS improvement
- Rate of early responders
- Rate of sustained responders
- Rate of remission in MADRS
- Changes from Baseline in single MADRS rating scale items
- Changes from Baseline in MADRS core mood items
- Change from Baseline in sleep onset latency
- Change from Baseline in REM sleep latency
- Change from Baseline in wake after sleep onset
- Change from Baseline in time spent in each sleep stage
- Change from Baseline in total sleep time
- Change from Baseline in sleep efficiency index
- Change from Baseline in number of awakenings
- Change from Baseline in number of sleep cycles

5.2.6. Secondary and Exploratory Analyses

CGI-S scores and change from Baseline will be summarized by treatment group and study visit. Differences between treatment groups in change from Baseline at Week 6 will be analyzed by means of an ANCOVA model run on ranked change, with treatment group as a factor and Baseline CGI-S value as a covariate.

CGI-I scores will be summarized by treatment group and study visit. Differences between treatment groups in CGI-I score at Week 6 will be analyzed by means of an ANCOVA model run on ranked score, with treatment group as a factor and Baseline CGI-S value as a covariate.

IDS-SR₃₀ total score and change from Baseline will be summarized by treatment group and study visit. Change from Baseline in IDS-SR₃₀ total score will be analyzed using an MMRM model with fixed effects for treatment group, region, visit, and treatment group-by-visit interaction, a random effect for patient within treatment group, and Baseline IDS-SR₃₀ total score as a covariate. Comparisons against placebo will be performed using the appropriate contrasts from this model at Week 6.

SHAPS total score and change from Baseline will be summarized by treatment group and study visit. Change from Baseline in SHAPS total score will be analyzed using an MMRM model with fixed effects for treatment group, region, visit, and treatment group-by-visit interaction, a random effect for patient within treatment group, and Baseline SHAPS total score as a covariate. Comparisons against placebo will be performed using the appropriate contrasts from this model at Week 6.

DSST score and change from Baseline will be summarized by treatment group and study visit. Change from Baseline in DSST score will be analyzed using an MMRM model with fixed effects for treatment group, region, visit, and treatment group-by-visit interaction, a random effect for patient within treatment group, and Baseline DSST score as a covariate. Comparisons against placebo will be performed using the appropriate contrasts from this model at Week 6.

PSS total score and change from Baseline will be summarized by treatment group and study visit. Change from Baseline in PSS total score will be analyzed using an MMRM model with fixed effects for treatment group, region, visit, and treatment group-by-visit interaction, a random effect for patient within treatment group, and Baseline PSS total score as a covariate. Comparisons against placebo will be performed using the appropriate contrasts from this model at Week 6.

A-SEX total score and change from Baseline will be summarized by treatment group and study visit. Change from Baseline in A-SEX total score will be analyzed using an MMRM

model with fixed effects for treatment group, region, visit, and treatment group-by-visit interaction, a random effect for patient within treatment group, and Baseline A-SEX total score as a covariate. Comparisons against placebo will be performed using the appropriate contrasts from this model at Week 6.

The rate of responders will be presented by treatment group and study visit. Treatment differences in responder rate at Week 6 will be analyzed using a logistic regression model with factors for treatment group and Baseline MADRS total score. Any patients who are missing Week 6 MADRS total score will have this value imputed using LOCF for this analysis.

Time to $\geq 50\%$ MADRS improvement will be summarized by treatment group using the Kaplan-Meier method. Treatment differences in time to $\geq 50\%$ MADRS improvement will be analyzed using a Cox-regression model with treatment group and Baseline MADRS total score as a covariate. If a patient does not experience $\geq 50\%$ improvement during the duration of the study, his or her time to $\geq 50\%$ MADRS improvement will be censored at the time of their last non-missing MADRS assessment.

Time to $\geq 30\%$ MADRS improvement will be summarized by treatment group using the Kaplan-Meier method. Treatment differences in time to $\geq 30\%$ MADRS improvement will be analyzed using a Cox-regression model with treatment group and Baseline MADRS total score as a covariate. If a patient does not experience $\geq 30\%$ improvement during the duration of the study, his or her time to $\geq 30\%$ MADRS improvement will be censored at the time of their last non-missing MADRS assessment.

The rate of early responders ($\geq 50\%$ and $\geq 30\%$ MADRS) will be presented by treatment group and study visit. Treatment differences in responder rate will be analyzed using a logistic regression model with factors for treatment group and Baseline MADRS total score. Any missing MADRS and CGI-I scores will be imputed using LOCF for this analysis.

The rate of sustained responders ($\geq 50\%$ and $\geq 30\%$ MADRS) will be presented by treatment group. Treatment differences in responder rate will be analyzed using a logistic regression model with factors for treatment group and Baseline MADRS total score. Any missing MADRS and CGI-I scores will be imputed using LOCF for this analysis.

The rate of remission in MADRS will be presented by treatment group. Treatment differences in remission rate will be analyzed using a logistic regression model with factors for treatment group and Baseline MADRS total score.

Single MADRS rating scale items and their change from Baseline will be summarized by treatment group and study visit. Differences between treatment groups in change from

Baseline to Week 6 will be analyzed using an ANCOVA of ranked data, with treatment group as a factor and Baseline rating value as a covariate.

MADRS core mood items and their change from Baseline will be summarized by treatment group and study visit. Differences between treatment groups in change from Baseline to Week 6 will be analyzed using an ANCOVA of ranked data, with treatment group as a factor and Baseline rating value as a covariate.

All changes in sleep parameters will be analyzed using an MMRM model with fixed effects for treatment group, region, visit, and treatment group-by-visit interaction, a random effect for patient within treatment group, and Baseline sleep parameter as covariate. Comparisons against placebo will be performed using the appropriate contrasts from this model at Week 6.

If the data is not amenable to analysis by logistic regression for any of the responder endpoints included in this section, then comparisons between treatment groups may be performed using Cochran-Mantel-Haenszel (CMH) testing instead.

5.3. PHARMACOKINETIC ANALYSES

The primary objective of the PK statistical analysis will be to estimate the relative bioavailability of MIN-117 and the effect of MIN-117 dose. Details of this analysis can be found in the PK Analysis Plan.

5.4. SAFETY ANALYSES

5.4.1. Adverse Events

Adverse events will be mapped to a Medical Dictionary for Regulatory Activities (MedDRA) version 21.0 preferred term and system organ classification. If a patient experiences multiple events that map to a single preferred term, the greatest severity grade and strongest investigator assessment of relation to study medication will be assigned to the preferred term for the appropriate summaries. Should an event have a missing severity or relationship, it will be classified as having the highest severity and/or strongest relationship to study medication.

The occurrence of TE adverse events (TEAEs) will be summarized by treatment group using preferred terms, system organ classifications, and severity. Separate summaries of TE serious adverse events (SAE), TEAE related to study treatment, TEAE leading to discontinuation of study treatment, and TE fatal adverse events will be generated. All adverse events reported will be listed for individual patients showing both verbatim and preferred terms, as well as system organ class. All adverse events that occurred prior to the

initiation of study treatment will be excluded from the tables but will be included in the listings. Any TEAE occurring after the End of Study visit will not be summarized.

Missing onset dates will be imputed as previously outlined in Section 3.3.5 as required to determine TE events. Adverse events occurring on Day 1 with missing onset times will be assumed to be TE.

5.4.2. Clinical Laboratory Assessments

Descriptive summaries of selected (quantitative) clinical laboratory results and change from baseline will be presented by treatment group and visit. Laboratory abnormalities will be determined using pre-defined normal ranges. The number and percentage of patients experiencing TE clinically significant (CS) laboratory abnormalities as reported by the central laboratory, and potentially clinically significant (PCS) abnormalities for select parameters per the table below will be summarized by treatment group. Additionally, shifts in Laboratory values with reference to the normal range from Study Baseline to Week 6 will be summarized by treatment group.

Listings will be provided for patients with any laboratory results outside the reference ranges, as well as for patients with any CS and PCS (select parameters) laboratory results.

Criteria for Potentially Clinically Significant Laboratory Tests

Laboratory Parameter	SI Units	Conversion Factor^a	Traditional Units	PCS Criteria^b Low Values	PCS Criteria^b High Values
Hematology					
Hemoglobin	F	g/L	0.1	g/dL	< 100
	Male				< 120
Hematocrit	F	ratio	100	%	≤ 32% and ≥3% decrease from baseline
	Male				≤ 37% and ≥3% decrease from baseline
White cell count		10 ⁹ /L	1	10 ³ /μL	≤ 2.5
Eosinophils absolute cell count		10 ⁹ /L	1	10 ³ /μL	—
Neutrophils absolute cell count		10 ⁹ /L	1	10 ³ /μL	≤ 1.50
					≥ 15
					≥ 1.50
					≥ 12.0

Lymphocyte absolute cell count	10 ⁹ /L	1	10 ³ /μL	≤ 0.8	≥ 4.0
Platelet count	10 ⁹ /L	1	10 ³ /μL	≤ 75	≥ 700
Chemistry					
Albumin	g/L	0.1	g/dL	< 28	—
Alkaline phosphatase	U/L	1	U/L	—	≥ 2 × UNL
ALT	U/L	1	U/L	—	≥ 3 × UNL
AST	U/L	1	U/L	—	≥ 3 × UNL
Blood urea nitrogen	mmol/L	2.8011	mg/dL	—	> 1.4 × UNL
Calcium	mmol/L	4.008	mg/dL	< 1.97	> 2.77
Cholesterol	mmol/L	38.6698	mg/dL	—	> 7.75
Creatinine	μmol/L	0.0113	mg/dL	—	> 1.4 × UNL
Glucose, fasting	mmol/L	18.015	mg/dL	< 3.0	> 7.6 × UNL
Potassium	mmol/L	1	mEq/L	< 3.3	> 5.5
Sodium	mmol/L	1	mEq/L	< 130	> 150
Total bilirubin	μmol/L	0.0585	mg/dL	—	> 1.5 × UNL
Urinalysis					
Protein	—	—	—	—	≥ 2 +
Glucose	—	—	—	—	≥ 1 +

^a Conversion factor is the multiplication factor to convert from SI units to traditional units.

^b Criteria refer to SI units.

LNL = lower normal limit of laboratory reference range; PCS = potentially clinically significant; SI = *Le Système International d'Unités* (International System of Units); UNL = upper normal limit of laboratory reference range.

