10.8.2. Clinical Laboratory Tests

Laboratory data will be summarized by type of laboratory test. Reference ranges and markedly abnormal results (specified in the SAP) will be used in the summary of laboratory data. Descriptive statistics will be calculated for each laboratory analyte at Baseline and at each scheduled time point. Changes from Baseline results will be presented in pre- versus post-treatment cross tabulations (with classes for below, within, and above normal ranges). A listing of patients with any laboratory results outside the reference ranges will be provided. A listing of patients with any markedly abnormal laboratory results will also be provided.

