1.2. TIME AND EVENTS SCHEDULE

Procedures and Evaluations	Screening	Baseline	Double-Blind Phase			Post Study Follow-Up
			3	4	5 / EW ^b	
Visit# ^a	1	2	3	4	5 / EW ^b	6
Week	-3	1	2	4	6	8
Day	-21 to -1	1	15	29	43	57
Screening/Administrative						
Informed consent	X					
Pharmacogenomic informed consent ^c	X					
Inclusion/exclusion criteria	X	X				
Medical history, SCID-5, MGH-SAFER	X					
Prior medications	X	X				
Preplanned surgery/procedures	X					
Height	X					
Pregnancy test ^d	X	X		X	X	X
Alcohol and Drug Screen	X	X				
TSH, serology	X					
Taper of psychotropic drugs	X ^e	X ^e				
Randomization		X ^f				
Study Drug						
Administer/Dispense study drug		X	X	X	X ^g	
Study drug accountability			X	X	X	
Pharmacokinetics						
Blood sample collection ^h		X	X	X	X	X
Pharmacodynamics						
Blood sample collection		X			X	
Pharmacogenomics						
Blood sample collection		X ⁱ				
Efficacy						
Investigator-Rated: MADRS, HAM-A, CGI-S	X	X	X	X	X	
Investigator-Rated: CGI-I			X	X	X	
Investigator-Rated: DSST		X	X	X	X	
Subject-Rated: SHAPS, A-SEX	X	X	X	X	X	
Subject-Rated: IDS-SR ₃₀	X	X			X	
Subject-Rated: PSS		X			X	
Sleep recording (Somno-Art) ^j	X	X			X	
Safety						
Physical examination	X	X			X	X
12-Lead ECG (triplicate) ^k	X	X		X	X	X
Vital signs, temperature, weight ^l	X	X	X	X	X	X
Clinical laboratory tests ^m	X	X			X	X
C-SSRS	X	X	X	X	X	X
Adverse Events	Continuous					
Concomitant therapy	Continuous					

Abbreviations: A-SEX = Arizona Sexual Experiences Scale; CGI-I = Clinical Global Impression of Improvement Scale; CGI-S = Clinical Global Impression of Severity Scale; C-SSRS = Columbia Suicide Severity Rating Scale; DSST = digit symbol substitution test; HAM-A = Hamilton anxiety scale; IDS-SR₃₀ = Inventory of Depressive Symptoms – Subject-Related; MADRS = Montgomery-Asberg Depression Rating Scale; PSS = Perceived Stress Scale; SCID-5 = Structured clinical interview for DSM-5; SHAPS = Snaith-Hamilton Pleasure Scale.

^aVisits 3 to 6 may occur within a ± 3 -day window relative to Baseline (Visit 2). Visit 2 may occur within a +7 day window relative to Visit 1 (i.e., the screening period may be extended to 28 days) upon Sponsor's decision.

^bVisit 5 represents the end-of-treatment or early withdrawal (EW) visit, and patients who discontinue the study prematurely should undergo all assessments indicated for this visit.

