3.3.7. Presentations by Time Point

Nominal Time Points as obtained from the CRF or laboratory will be utilized for summary displays. If assessments are collected multiple times within a given nominal time point, the result closest to the scheduled time will be used for summary presentations. If two measurements have the same distance to the expected time, the earlier value will be used. If a scheduled assessment and an Unscheduled or Early Termination assessment are collected on the same day, the scheduled assessment will be used for summary presentations, unless

otherwise indicated by the sponsor. Unscheduled and Early Termination assessments will be windowed to a study visit using the analysis window described below in case the scheduled visit was not performed. All assessments will be presented in the listings.

Visit	Target Day	Window Days
3: Week 2	15	9 - 22
4: Week 4	29	23 - 36
5: Week 6	43	37 - 50
6: Follow-Up	57	51 - 64

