 - 14.3.1.5 Treatment-Emergent Fatal Adverse Events by System Organ Classification and Preferred Term, Safety Population
 - 14.3.2.1 Treatment-Emergent Serious Adverse Events by System Organ Classification and Preferred Term, Safety Population
 - 14.3.4.1 Clinical Laboratory Hematology Parameters by Time Point, Safety Population
 - 14.3.4.2 Clinical Laboratory Chemistry Parameters by Time Point, Safety Population
 - 14.3.4.3.1 Clinically Significant Laboratory Values, Safety Population
 - 14.3.4.3.2 Clinically Significant and Potentially Clinically Significant Laboratory Values, Safety Population
 - 14.3.4.4 Clinical Laboratory Parameter Shifts from Study Baseline to Week 6, Safety Population
 - 14.3.5.1 Vital Signs by Time Point, Safety Population
 - 14.3.5.2.1 Patients with Clinically Significant Vital Signs Occurring Post-Baseline, Safety Population
 - 14.3.5.2.2 Patients with Clinically Significant or Potentially Clinically Significant Vital Signs Occurring Post-Baseline, Safety Population
 - 14.3.5.3.1 12-Lead ECG Assessments by Time Point, Safety Population
 - 14.3.5.3.2 Summary of QTcF (msec) Categories, Safety Population
 - 14.3.5.4 Patients with Significant ECG Abnormalities Occurring Post-Baseline, Safety Population
 - 14.3.6.1 Summary of C-SSRS by Visit, Safety Population

Data Listings

- 16.2.1 Patient Disposition
 - 16.2.2.1 Protocol Deviations
 - 16.2.2.2 Inclusion/Exclusion Criteria
 - 16.2.4.1 Demographics
 - 16.2.4.2 Medical and Surgical History
 - 16.2.5.1 Study Drug Administration
 - 16.2.5.2 Prior and Concomitant Medications
 - 16.2.5.3.1 Pharmacokinetic Plasma Concentrations
 - 16.2.6.1 MADRS Rating Scale
 - 16.2.6.2 CGI-S and CGI-I Questionnaires
 - 16.2.6.3 HAM-A Questionnaires
 - 16.2.6.4 IDS-SR₃₀ Questionnaires
 - 16.2.6.5 SHAPS Questionnaires
 - 16.2.6.6 DSST Questionnaires
 - 16.2.6.7 PSS Questionnaires
 - 16.2.6.8 A-SEX Questionnaires
 - 16.2.6.9 C-SSRS Questionnaires
-

16.2.6.10	Somno-Art Sleep Parameters
16.2.7	Adverse Events
16.2.8.1.1	Laboratory Data – Chemistry
16.2.8.1.2	Laboratory Data – Hematology
16.2.8.1.3	Laboratory Data – Urinalysis
16.2.8.1.4	Laboratory Data – Other
16.2.8.1.5	Laboratory Results Outside Reference Range
16.2.8.1.6	Potentially Clinically Significant Laboratory Results
16.2.8.2.1	Vital Signs
16.2.8.2.2	Weight, Height and BMI
16.2.8.3	Physical Examinations
16.2.8.4	12-Lead ECG Findings

Figures

14.2.1.1.5	Change from Baseline in MADRS by Visit, ITT Population

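### The only laboratory shift table stops at Week 6, so an early-termination panel taken before Day 37 is left out under the SAP's day-windowing rule; the SAP should add a shift to the Visit 5/EW value.

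*SAP*

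**What the plan says.** **Shift table.** SAP 5.4.2 states that "shifts in Laboratory values with reference to the normal range from Study Baseline to Week 6 will be summarized by treatment group". The matching output in SAP section 9 is Table 14.3.4.4, "Clinical Laboratory Parameter Shifts from Study Baseline to Week 6, Safety Population". No other laboratory shift table is listed.

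**Visit assignment.** SAP 3.3.7 begins with a general rule: "Nominal Time Points as obtained from the CRF or laboratory will be utilized for summary displays". It then gives a specific one: "Early Termination assessments will be windowed to a study visit using the analysis window described below in case the scheduled visit was not performed". The windows are Week 2 = Days 9-22, Week 4 = Days 23-36, Week 6 = Days 37-50 and Follow-Up = Days 51-64.

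**When laboratory samples are taken.** The Time and Events Schedule marks clinical laboratory tests at Screening, Baseline, Visit 5/EW and Visit 6. Visits 3 (Week 2) and 4 (Week 4) are blank. Its footnote b says that "patients who discontinue the study prematurely should undergo all assessments indicated for this visit", so an early withdrawer should have an end-of-treatment panel.

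**Protocol.** Section 10.8.2 says: "Changes from Baseline results will be presented in pre- versus post-treatment cross tabulations". It does not say which post-treatment value is meant.

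**Other laboratory outputs.** SAP 5.4.2 also plans by-visit summaries, counts of treatment-emergent clinically significant (CS) abnormalities as reported by the central laboratory, counts of potentially clinically significant (PCS) abnormalities for selected parameters, and listings of out-of-range results.

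**The concern.** SAP 4.2 bases the safety analyses on every treated patient, and Table 14.3.4.4 carries the Safety Population label. The windowing rule nevertheless excludes from that table end-of-treatment panels that the study sets out to collect.

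The exclusion is tied to early withdrawal, which is unlikely to be unrelated to tolerability. Protocol 9.2 lists laboratory criteria and adverse events among the reasons for withdrawal. If withdrawal before Day 37 differs between arms, the shift rates being compared come from differently selected subsets of each arm.

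The by-visit tables have a related problem. A Week 2 or Week 4 laboratory row would consist only of early-termination and unscheduled panels, and could not be compared with the Baseline or Week 6 rows.

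**Working it through.** **1. Map each day to a window (SAP 3.3.7) and to the laboratory schedule.**

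| Study day of early-termination panel | Days | Window | Panel scheduled at that visit? |
|---|---|---|---|
| 2-8 | 7 | none | - |
| 9-22 | 14 | Week 2 | no |
| 23-36 | 14 | Week 4 | no |
| 37-50 | 14 | Week 6 | yes |
| 51-64 | 14 | Follow-Up | yes |

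Days before the Week 6 window: 7 + 14 + 14 = 35. None of the 35 maps to Week 6.

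**2. Refinements.**
- Windowing applies only if the scheduled visit was not performed. A patient seen at Visit 3 on Day 15 and withdrawn on Day 20 may therefore have a panel that goes to no visit. It is still not Week 6.
- The date that counts is that of the assessment. A patient who stops treatment earlier but is assessed on Day 37 or later is included.
- The post-study draw about two weeks after early withdrawal may fall on Days 37-50. It is nominal Visit 6, and the windowing sentence covers only unscheduled and early-termination assessments, so it does not become a Week 6 value.

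**3. What the PCS counts cover.** Protocol 8.6 lists 23 serum chemistry analytes. TSH is tested at Screening only, which leaves 22. The PCS table in SAP 5.4.2 has limits for 12 of them. 22 - 12 = 10 have none: chloride, GGT, CPK, LDH, uric acid, phosphorus, total protein, triglycerides, HDL and LDL. Where limits exist they can lie well beyond the normal range. For ALT and AST the limit is 3 times the upper normal limit, so a normal-to-high shift below that is not a PCS event.

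**4. What happens to the liver stopping criteria.** Protocol 9.2 uses ALT above 5 times the upper limit, or bilirubin above 2 times with ALT above 3 times (and alkaline phosphatase below 1.5 times). The PCS limits are ALT at or above 3 times and bilirubin above 1.5 times. Every patient meeting a liver stopping criterion therefore also meets a PCS limit, and the PCS count is not tied to Week 6.

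**5. Number of patients.** The documents give no early-withdrawal rate. The 10% in the sample-size section is for patients lacking Baseline or post-Baseline efficacy data, which is a different quantity. Assumed share r with an early-withdrawal assessment before Day 37, times 324:

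| r (assumed) | All (324) | Placebo (162) | Each MIN-117 arm (81) |
|---|---|---|---|
| 5% | 16.2 | 8.1 | 4.1 |
| 10% | 32.4 | 16.2 | 8.1 |
| 20% | 64.8 | 32.4 | 16.2 |
| 30% | 97.2 | 48.6 | 24.3 |

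These are upper figures for each r. A patient with no early-withdrawal panel cannot be recovered by any table definition.

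**6. Effect on a shift rate.** Let f be the share of an arm with an excluded panel, and let p_w and p_c be the shift rates in those patients and in the rest. The table reports p_c; the rate in all patients with a panel is p_c + f(p_w - p_c). The understatement is f(p_w - p_c), which is zero if the two rates agree. Invented example: in an arm of 81, 12 patients have excluded panels, 3 of them shifted, and 2 of the other 69 shifted. The table shows 2/69 = 2.9%; the full rate is 5/81 = 6.2%. Check: (12/81) x (25.0% - 2.9%) = 3.3 percentage points.

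**The case against.** **The nominal label may already solve it.** The schedule has one combined 5/EW column, SAP 3.3.8 defines the study visit as the nominal CRF visit, and the same section refers to a Visit 5/Early Termination CRF. If every early-withdrawal panel is recorded under that visit, the opening rule of SAP 3.3.7 could place it at Week 6. This stands as an ambiguity. The sentence written specifically for early-termination assessments points the other way, and a specific rule normally governs. If the nominal reading was intended, the SAP has to say so, because two programmers could produce different tables.

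**Serious signals are not hidden.** This stands. A reader might infer that patients stopped for a laboratory abnormality disappear from the safety report. The documents do not support that. Patients meeting the liver stopping criteria exceed PCS limits and are counted. The CS count (Table 14.3.4.3.1) is not restricted to selected parameters or to Week 6. Protocol 8.6 requires clinically relevant laboratory changes to be recorded as adverse events, and Listing 16.2.8.1.5 shows out-of-range results. The remaining gap is that the SAP gives no criteria for CS, a CS count is not a shift against the normal range, and a listing gives no group rate.

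**The protocol is not contradicted.** A reader might also infer that the SAP breaks a commitment in Protocol 10.8.2. That section does not name the post-treatment value, and Baseline to Week 6 is one admissible cross-tabulation. It is a narrower choice, not a breach.

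**The size is assumed.** This stands. Neither the patient counts nor the 2.9% versus 6.2% example rests on a documented rate.

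**Conclusion.** The point holds in limited form. Under the SAP's specific rule for early-termination assessments, a panel dated Days 2-36 does not enter the only laboratory shift table, and in the by-visit tables it is dropped or put at a visit with no scheduled panel. The loss is confined to those tables. It concerns mainly the group-level rate of milder normal-to-abnormal shifts, including for the 10 chemistry analytes without PCS limits.

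It would go too far to say that every patient who withdraws before Day 37 is lost. The assessment date decides, and the nominal-visit reading remains open until the SAP closes it.

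The number affected is unknown: about 16-97 of 324 if 5-30% have their early-withdrawal assessment before Day 37, fewer where no panel was taken. Any distortion between arms also requires that excluded patients shift at a different rate from the others, and that their share or their rate differs by arm. The change is still worth making, because the data are to be collected anyway and the omission is linked to withdrawal.

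**What to change.** Before database lock and unblinding:

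1. In SAP 5.4.2 and Table 14.3.4.4, define the shift as Baseline to the last on-treatment value, meaning the Visit 5/EW panel, with early-termination panels included whatever their study day. A worst post-Baseline panel is an optional addition.
2. Keep Baseline to Week 6 as a second panel of the same table.
3. In the by-visit laboratory tables, show early-withdrawal panels in an end-of-treatment (Visit 5/EW) row instead of windowing them to Week 2 or Week 4.
4. State in SAP 3.3.7 whether the nominal visit or the day window governs early-termination laboratory panels.

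**Cost.** A few lines of SAP text and one extra table panel; no new data. End-of-treatment values mix different lengths of exposure, which is why the Week 6 panel should stay. The optional worst-value panel would show somewhat more abnormalities in every arm and would bring in repeat tests ordered on suspicion.
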